6.3 SAFETY MEASURES

We will be monitoring the safety of our participants throughout the study with the following measures. These measures are listed below and can be found in the attached documents.

- A. A stimulation adverse effects questionnaire used in previous studies (IRB #14-1622, #14-3285, and #14-0600) will be administered at the end of each stimulation session. This questionnaire will be used as a safety measure and to collect data on participant experience. Please see *9.1 Safety Parameters* for more information.

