10.1 SAFETY PARAMETERS

STIMULATION SIDE EFFECTS. A stimulation adverse effects questionnaire used in previous studies will be administered at the end of each stimulation. This questionnaire will be used as a safety measure and to collect data on participant experience. The adverse effects questionnaire asks participants to respond on a 4 point Likert scale on the severity of symptoms experienced during the stimulation session (1 = absent, 2 = mild, 3 = moderate, 4 = severe). The side effects listed are headache, neck pain, scalp pain, tingling, itching, ringing/buzzing noise, burning sensation, local redness, sleepiness, trouble concentrating, improved mood, worsening of mood, dizziness, flickering lights, and other (specify). Participants are also asked to rate on a 5 point Likert scale how related they believe the side effects to be to stimulation (1 = no relation, 2 = remote, 3 = possible, 4 = probable, 5 = definite).

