10.2 METHODS AND TIMING FOR ASSESSING, RECORDING, AND ANALYZING SAFETY PARAMETERS

10.2.1 ADVERSE EVENTS

All AEs, including local and systemic reactions not meeting the criteria for “serious adverse events”, will be captured on the appropriate CRF. In addition, the AE Report Form will be completed by the study coordinator (Appendix B). The AE Report Form includes the following:

- What is known about the therapy
- What is known about previous reported side effects
- If the AE occurred in temporal relation to the therapy
- Whether or not the AE improves or disappears when treatment is stopped
- Whether the AE is worsening of baseline symptoms
- Whether the AE is related to concurrent medical condition or medication use

Once complete, this form will be given to the PI, who will review, comment, and sign this form. Completed forms will be placed in the participant’s folder.

In addition, the study coordinator will document any AE occurrence on the AE log (*Appendix D*), which includes information such as the date of the AE, severity, relationship to the treatment (assessed by the PI*), actions taken, and outcome(s). The log will be reviewed and initialed by the PI 72 hours after being completed. All AEs will be followed to adequate resolution and will be graded for severity and relationship to study. Any medical condition noted at the stimulation session will be considered at baseline and not reported as an AE.

***Relationship to Study Products:** The PI will determine whether an AE is associated with the study treatment. The event will be labeled associated if the event is temporally related to the administration of a therapy and no other factors can explain the event. The event will be labeled as not associated if the event is temporally independent of the study treatment and can be explained by external factors, such as major life events.

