APPENDIX A: SCHEDULE OF EVENTS

	Telephone Screening Interview	Session 1: Screening	Session 2: Baseline	Sessions 3 & 4: Stimulation
Procedures				
Provide Verbal Consent	x			
Signed Consent Form		x		
Assessment of Eligibility Criteria	x	x		
Urine Pregnancy Test		x		
Baseline Self-Report Assessments			x	
Baseline EEG (Resting state)			x	x
Cognitive control task		x	x	x
Task EEG (during cognitive control task)			x	x
Stimulation during task				x
Stimulation Questionnaire				x

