APPENDIX B: AE REPORT FORM

Adverse Effects Report:

Reasons for Report (adverse event, time, date and place of occurrence if available):

1. What do we already know about the stimulation?
 - a.
2. What is the temporal relationship of the AE to the stimulation?
 - a.
3. Does the AE improve or disappear when the stimulation is stopped?
 - a.
4. Is the AE a worsening of baseline symptom(s)?
 - a.
5. Is the AE a result of an underlying concurrent medical condition(s) or concurrent medication(s)?
 - a.
6. Additional Information provided by research team
 - a.

Research team member signature _____ Date _____

Co-Investigator:

CONFIDENTIAL

Steps to be taken (if applicable)

Co-I signature _____ Date _____

PI Comments:

Steps to be taken (if applicable)

PI signature _____ Date _____

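### The side-effects questionnaire is given only after stimulation, so attribution is subjective and the AE form's baseline item lacks a same-scale reference for most symptoms

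*Combined protocol and SAP*

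**What the plan says.** **Timing.** Section 6.3 states that the questionnaire "will be administered at the end of each stimulation session. This questionnaire will be used as a safety measure and to collect data on participant" (what they experienced). Section 10.1 repeats the timing: "A stimulation adverse effects questionnaire used in previous studies will be administered at the end of each stimulation". In the Appendix A schedule, the row "Stimulation Questionnaire" has one mark, under Sessions 3 and 4, and none under Screening or Baseline.

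**Content.** By Section 10.1 the form has 15 items (14 named, plus an open one), each scored from 1 (absent) to 4 (severe). It asks "on the severity of symptoms experienced during the stimulation session". A separate five-point item asks how strongly the participant believes the effects were related to stimulation.

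**Attribution.** Section 10.2.1 (Adverse Events) has the PI decide whether an event is associated with the study treatment. The Appendix D log offers four relationship grades, two of which point away from the device.

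**Baseline.** Section 10.2.1 lists among the contents of the AE report form "Whether the AE is worsening of baseline symptoms", and the Appendix B form carries the same question. The section also treats a medical condition noted at the stimulation session as baseline rather than as an AE, without naming an instrument or a time point.

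**The concern.** The recall window is the whole session. It therefore covers the EEG net and a long memory task as well as TMS. Headache, scalp or neck pain, sleepiness and poor concentration could plausibly come from the net, the task or the participant's state on arrival. One rating at the end cannot tell these sources apart, and the plan collects no other rating on the same scale.

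Two uses of the data suffer. The description of what participants experienced cannot show how much of it exceeds the task and net alone. The AE form's baseline question must be answered, for most listed symptoms, from memory or informal history. Error can run either way: a symptom present on arrival may be scored as a side effect, or a new one may be filed as baseline.

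**Working it through.** The plan states no side-effect rate, so there is no figure to reproduce. The check is mainly textual, with a short illustration.

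**1. Is there a comparator without TMS inside Sessions 3 and 4?** No. Section 5.2 delivers stimulation on every trial. The control in Section 11.1 is arrhythmic TMS, which is still TMS. Section 4.1 mixes the three frequencies within every block, so an end-of-session score cannot be split by frequency either.

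**2. Is there one elsewhere?** Session 2 has the task and the net without rhythmic trains (Sections 4 and 5.2, Appendix A). The questionnaire is not scheduled there.

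**3. What supports the attribution?**
- The participant's relatedness rating is a belief, held by someone who had pulses on every trial.
- The PI calls an event associated if it coincides with treatment and nothing else can explain it. It is not associated if it is unrelated in time and has an outside explanation. A headache that starts during the session and that the net could also explain fits neither definition.
- Appendix D lets the PI grade the event as unlikely or unrelated, but supplies no evidence for that choice.

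**4. What baseline information exists?**

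| Source | Covers | Limit |
|---|---|---|
| TMS screening questions (6.1) | Ringing in the ears | Not a rating on this scale |
| Session 2 self-reports (5.2, 6.1) | Anxiety, affect, depression | Not repeated at Sessions 3 and 4; may be completed remotely beforehand |
| Baseline rule (10.2.1) | Medical conditions noted at the session | No instrument or time point |

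None of these rates headache, neck or scalp pain, tingling, itching, sleepiness or trouble concentrating on the same scale.

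**5. Illustration of size.** Inputs: n = 48 completers (Section 11.2) and an assumed background rate b, with no TMS effect. Expected number of positive reports = 48 × b:
- b = 0.10: 48 × 0.10 = 4.8, about 5
- b = 0.30: 48 × 0.30 = 14.4, about 14
- b = 0.50: 48 × 0.50 = 24

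**6. What a Session 2 rating could show.** Assume independence between sessions within a person and no TMS effect. The 95% half-width for the paired difference in rates is 1.96 × √(2b(1 − b)/48):
- b = 0.10: 1.96 × √(0.18/48) = 0.120
- b = 0.30: 1.96 × √(0.42/48) = 0.183
- b = 0.50: 1.96 × √(0.50/48) = 0.200

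The comparison would be coarse, about 12 to 20 percentage points either side, which suits description rather than testing.

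**7. How clean is Session 2 as a reference?** Not fully. It always precedes Sessions 3 and 4. Task length is also inconsistent: Section 6.2 gives 600 trials per stimulation session, while Section 6.5.1 gives 10 blocks of 20 to 30, that is 10 × 20 = 200 to 10 × 30 = 300. Section 6.2 further describes stimulation at all four sessions and rhythmic trains at three, against two stimulation sessions in Sections 4 and 5.2 and Appendix A.

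**The case against.** A reader might infer that every task or net symptom will be counted as a TMS effect. The documents do not support that. The relatedness item, the PI's rule and the Appendix D grades all allow a symptom to be judged unrelated. Staff also check on participants during stimulation (Sections 8.2.1 Physical and 8.3), which can help date onset, and moderate or severe reports prompt a discussion (Section 8.3).

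A reader might also infer that there is no baseline at all. That goes too far, given the sources tabulated above. The Appendix B item is free text for any AE, and nothing ties it to this questionnaire, so staff could answer it from history.

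It can further be said that the trial has no safety endpoint. Section 2.3 names working memory capacity, spectral power and response time, and Section 11.1 plans no comparison of side effects. For monitoring, capturing too much is the safer error. The remedy is also imperfect: an arrival rating comes before both net and task, so change from arrival still mixes them with TMS, and Session 2 is confounded with session order.

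All of this stands, and it limits the point to a modest improvement. It does not supply the missing reference: the safeguards record judgements without giving a symptom-level rating to base them on. Section 6.3 itself assigns the form a descriptive purpose beyond monitoring.

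**Conclusion.** The point holds as a minor one. The schedule is clear, and most listed symptoms have no same-scale rating before stimulation or in the session without rhythmic trains. Attribution therefore rests on belief and judgement.

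It does not follow that reported side-effect rates are biased upward by a known amount. The counts of 5, 14 and 24 out of 48 depend wholly on assumed background rates of 10%, 30% and 50%; they are symptom reports, not effects attributed to TMS. That the net or task produces such symptoms is plausible but is not stated in the documents. The form is described as an attachment and was not available here, so its layout could not be checked. No primary or secondary outcome is affected.

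**What to change.** In Sections 6.3 and 10.1 and in Appendix A:

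- Give the existing questionnaire on arrival at Sessions 3 and 4, with the recall wording adapted to current symptoms. Use it to answer the baseline item on the AE form, and report change from arrival. This removes only symptoms already present.
- Give it at the end of the Session 2 task, before any motor-threshold pulses. Report the within-person comparison with Sessions 3 and 4 descriptively, with intervals, and state that Session 2 always comes first.
- Reconcile Section 6.2 with Sections 4 and 5.2 and Appendix A on which sessions involve stimulation, and with Section 6.5.1 on the number of trials. Until then it is unclear which sessions the Section 10.1 wording covers and how far task exposure in Session 2 matches Sessions 3 and 4.

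The cost is one 15-item form three more times per participant, a few minutes per session, and the matching schedule entries.

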6.4 LABORATORY EVALUATIONS

6.4.1 SCREENING LABORATORY EVALUATIONS

A urine pregnancy test will be performed for all female participants.

INSTRUCTIONS FOR SPECIMEN PREPARATION, HANDLING, AND STORAGE. For this evaluation, an FDA approved commercial home-based kit will be used (HCG Urine Pregnancy Test Strip). Results are available after only a few minutes. Once the results are clear, the researcher will make a note and the sample will be disposed. All samples will be handled using single-use disposable medical gloves.

6.5 COGNITIVE TASKS

6.5.1 COGNITIVE CONTROL TASK

The cognitive control task used in this paradigm consists of the presentation of colored squares on the left and right side of a computer screen. Stimuli are presented briefly, followed by a brief delay. After this, an arrow pointing to the left, right, or both left and right will briefly appear on the screen. This informs the participants which set of squares (left or right) they must remember and will be tested on. The cue is followed by another delay, and finally a new set of squares is presented. Participants press a button to indicate whether the squares are the same or different from the ones they originally saw. Between presentation of stimuli there is a small centrally presented fixation cross upon which participant maintain their gaze. Participants will complete 10 blocks of the task, each composed of 20-30 trials each. Participants will have a self-paced break between each of the blocks.

7 STUDY INVESTIGATIONAL PRODUCT

We will use the MagPro X100 system (MagVenture Inc., Alpharetta, Georgia, USA) for transcranial magnetic stimulation. The MagPro X100 is an advanced, high performance magnetic stimulator designed primarily for research purposes. It is a high-quality tool for researchers with a large choice of stimulating parameters and has stimulation rates up to 100 pulses per second at high intensities and the possibility to combine waveforms and pulse modes.

The simulator has several features:

- 3 waveforms: Biphasic, Biphasic Burst and Monophasic.
- Selectable current direction.
- Stimulation rates up to 100 pulses per second.
- Easily connects to external equipment via programmable input/output triggers.
- System operation control via a built-in computer, eliminating the need for an external computer to set up and control the timing of stimulus sequences.
- Controllable from an external device.

7.1 SAFETY FEATURES

In the USA, federal law regulates the sale of Medical Devices through the US Food and Drug Administration (FDA). This is done to ensure safety and effectiveness. Devices which are permitted to be marketed for their intended use must either have a 510(k) or PMA clearance.

MagPro® stimulators R20, R30, R30 with MagOption, X100, and X100 with MagOption are all FDA 510(k) cleared (k160280, k061645, k091940 and k150641).

k150641: The intended use is treatment of Major Depressive Disorder in adult patients who have failed to receive satisfactory improvement from prior antidepressant medication in the current episode.

k160280, k061645, k091940: The intended use is for stimulation of peripheral nerves for diagnostic purposes.

The use of devices for other than their FDA cleared intended use is considered as investigational. Such use is only permitted if the Investigational Device Exemption (IDE) guidelines have been followed. For full information on this procedure, please consult FDA's website (www.fda.gov).

All investigational devices must be labeled in accordance with the labeling provisions of the IDE regulation (§ 812.5) and must bear a label with this statement:

"CAUTION Investigational Device. Limited by Federal (or United States) law to investigational use."

7.2 PREPARATION AND ADMINISTRATION OF STUDY INVESTIGATIONAL PRODUCT

After participants have completed the questionnaire, they will be comfortably seated. The study coordinator and/or the research assistant will be thoroughly trained and have trainings documented on the transcranial magnetic stimulation device and will be present during all stimulation sessions. To monitor side effects of stimulation, a questionnaire will be administered after each stimulation.

7.3 ASSESSMENT OF PARTICIPANT COMPLIANCE WITH STUDY INVESTIGATIONAL PRODUCT

Compliance for this study is determined as completion of all four sessions.

8 POTENTIAL RISKS AND BENEFITS

8.1 BENEFITS TO PARTICIPANTS AND SOCIETY

This research has the potential to provide critical data for understanding the neural basis of cognitive control. The current study has no immediate benefit to the healthy participants that participate. However, the results of this study may be used to develop novel tools for the treatment of psychiatric mood-disorders that involve a detriment in cognitive control. Furthermore, simultaneous neuro-imaging with brain stimulation will provide increased understanding of the neural mechanisms that underlie the efficacy of brain stimulation.

8.2 POTENTIAL RISKS

8.2.1 PSYCHOLOGICAL

Risk of Embarrassment: Self-report questionnaire contains questions regarding personal information. This risk is necessary in order to assess symptomology and associated psychopathology. Participants will be assured upon intake that only study personnel will see any answers.

Risk of Confidentiality Breach. To avoid breaches in confidentiality, study documents that contain personal information, including the informed consent, and the document that links study ID numbers to personal identifying information are kept in locked filing cabinets in locked rooms, separate from any source documents containing participating dummy identifiers. All data is stored in locked cabinets inside locked offices; electronic data will be stored only on password-protected computers, and data encryption methods will be used during communication between investigators. Only study personnel will have access to these data. All study staff participate in annual human participating training that includes education about responsibilities to minimize the risk of confidentiality breach. In the unlikely event of a breach of confidentiality, people might discover that an individual was involved in this research study and some people might not agree with the principle of participating in research or of changing natural brain activity.

8.2.1 PHYSICAL

Risk of Injury and Discomfort: Transcranial magnetic stimulation has been cleared for use in the USA by the FDA. TMS (the methodology used in this experiment) has nothing to do with electroconvulsive therapy that applies many orders of magnitude higher stimulation current. The level of electrical stimulation produced by TMS is within the range of activity that is endogenous to the brain. Furthermore, the intensity of stimulation is calibrated to the sensitivity of the individual participant such that the level of stimulation is matched to that of naturally occurring activity. In order to monitor side-effects, we will be administering an adverse effects stimulation questionnaire after each stimulation session to determine whether these effects were experienced. Research personnel present during these sessions will also check with the participant periodically during the stimulation to see whether they are comfortable. If any side-effect occurs (rated by the participant as stronger than “moderate”) or the participant is experiencing severe discomfort, the stimulation will be immediately stopped.

8.3 REFERRALS FOR MEDICAL FOLLOW-UP OR PSYCHOLOGICAL COUNSELING

There is a purely theoretical likelihood that stimulation of neuronal circuits can lead to epileptic discharge. To minimize this occurrence, we screen and exclude participants with personal and family history of neurological conditions from the study. If abnormalities or a seizure is witnessed during the course of the study, a referral will be made to the UNC Department of Neurology for follow-up. In the theoretical event that a seizure is witnessed that involves the loss of consciousness, the participants will be told not to operate a motor vehicle until cleared by the DMV.

CONFIDENTIAL

To ensure participant comfort, a study coordinator or research assistant will periodically check in with the participant about any side-effects he/she may be experiencing during each stimulation session. Following the conclusion of the stimulation session, the participant will receive an Adverse Effects Questionnaire to report on any of the side-effects he/she may have experienced. This questionnaire reports side-effects on a Likert scale (1=Absent, 2=Mild, 3=Moderate, 4=Severe). If the participant reports side-effects of Moderate to Severe intensity, a study coordinator or research assistant will discuss the side-effects experienced and note this response. The medical monitor will be contacted based on the reported intensity on the Adverse Events Questionnaire and the participant's verbal confirmation of intensity.

9.3.1 PREGNANCY FOLLOW-UP

Pregnancy tests will be administered on the first session of the experiment to all female participants. After testing negative, the experiment can continue. On subsequent sessions, female participants will be asked if it is possible that they may have become pregnant since the previous session. If the participant responds yes, or is unsure, then a pregnancy test will be administered. After testing negative at a given session (meeting inclusion criteria), if a participant reports becoming pregnant during the course of the study, she will be withdrawn from further participation. There are no plans to follow participants who become pregnant while enrolled in the study.

9 DATA AND SAFETY MONITORING

9.1 [name] LAB MONITORING PLAN

The purpose of this monitoring plan is to present the [name] Lab's approach to monitoring clinical trials. The plan facilitates compliance with good clinical practice (GCP):

- a. The rights and well-being of human participants are protected.
- b. The reported trial data are accurate, complete, and verifiable from source documents
- c. The conduct of the trial is in compliance with the currently approved protocol/amendment(s) with GCP, and with applicable regulatory requirement(s)

This section identifies key monitoring activities and specifies the data to be reviewed over the course of a clinical trial. This is a single site, investigator-initiated, clinical trial, so there will be no site monitoring plan in place. The latest version of the approved IRB application for this clinical trial will be followed at all times. This responsibility falls into the hands of the study coordinator and research assistants. If at any time there is a deviation from protocol, the deviation from protocol log will be filled out. All team members will be trained on how and when to use this log. The most up-to-date IRB application will be on file in the Clinical Trials office in [name]. Deviations will be sent to the IRB every 4-6 weeks (if necessary). Periodically, study staff should review 3 randomly selected informed consent forms to ensure that (1) these forms have been filled out appropriately, and (2) the consent form process was followed and properly documented. Should any consent form be in violation, the research team will perform and document a complete review of all consent forms.

AE and SAE are clearly defined in this document. Documents of AE and SAE can be found in the study binder on file in the Clinical Trials office in [name]. It is the responsibility of the study coordinator to report all events to the PI in a timely manner. All AEs and SAEs will be discussed with the PI. For our practices, we have adapted the decision tree provided by the UNC-CH IRB to assist with reporting of such events.

